14.0 Body Fluid Biospecimens

14.1 Body Fluid Biospecimen Submission

14.11 Summary Table of Body Fluid Specimens for This Protocol

Type of biospecimen to submit	Mandatory or optional	When to submit	Reason for submission (background/methodology section)	Where to find specific details for specimen submission
Blood/blood products (EDTA whole blood)	Mandatory	Multiple draws (see Section 14.21 for schedule)	Defined translational studies (Section 14.211)	Section 14.2
Blood/blood products (EDTA whole blood)	Mandatory	Baseline Prior to Treatment and Multiple Draws	Banking (Section 14.212)	Section 14.2

- 14.12 Kits are required for this study.
- 14.121 The kit contains supplies and instructions for collecting, processing, and shipping specimens.
 - 14.122 Participating institutions may obtain kits by completing and faxing the Supply Order Form (found in the Forms Packet) to the number listed on the form. Fill out the site address to where the kits will be shipped on the Fax Supply form. Because we are now being charged for all outgoing kits, a small, but sufficient, supply of the specimen collection kits should be ordered prior to patient entry. **Do not send the unused kits back to Biospecimen Accessioning and Processing (BAP) Receiving or the BAP Shared Resource.**
 - 14.123 Kits will be sent via FedEx® Ground at no additional cost to the participating institutions. **Allow at least two weeks to receive the kits.**
 - 14.124 Kits will not be sent via rush delivery service unless the participating institution provides their own FedEx® account number or alternate billing number for express service. **ACCRU will not cover the cost for rush delivery of kits.**
- 14.13 All samples must be collected Monday –Friday.
- 14.14 Label specimen tube(s) with protocol number, ACCRU patient ID number, and time and date blood is drawn and sample type.
- 14.15 Collect and process all blood/blood products according to the directions below and the kit instructions for the table below.
- 14.151 Baseline and Cycle 2 EDTA Tube: Centrifuge the EDTA tubes in a refrigerated centrifuge within 2 hours or less after collection all time points. Centrifuge sample 3000 rpm x 10 minutes. Carefully pipette 1.0 mL of plasma into each of the 3 cryovials. Next pipette the white blood cells being careful to not disturb the underlying cell layer into the 4th cryovial. Carefully tighten the caps. Discard the EDTA collection tube.
 - 14.152 Serial Draws: Centrifuge the EDTA tubes in a refrigerated centrifuge within 2 hours or less after collection all time points. Centrifuge sample 3000 rpm x 10 minutes. Carefully pipette 1.0 mL of plasma into each of the 3 cryovials. Carefully tighten the caps. Discard the EDTA collection tube.

14.153 Freeze all cryovials at -70°C or colder until shipped.

Indicate if specimen is mandatory or optional	Collection tube description and/or additive (color of tube top)	Volume to collect per tube (number of tubes to be collected)	Blood product being processed and submitted by participating site	Baseline, Prior to Tx	Cycle 1, Day 7 Prior to Tx, Cycle 1 Day 14 Prior to Tx, Cycle 1 Day 21 prior to Tx	Cycle 2 Day 1 Prior to Tx and Cycle 2 Day 21 Prior to Tx	Additional processing required at site after blood draw?	Storage /shipping conditions
Mandatory	EDTA	10 ml (1)	Plasma (PK)		X	X	Yes	Freeze/dry ice
Mandatory	EDTA	10 ml (1)	Plasma, White Blood Cells (banking)	X		X	Yes	Freeze/dry ice

14.16 Shipping

- 14.161 Verify ALL sections of the Blood Specimen Submission Form (see Forms Packet), BAP Requisition Form (provided in kit), and specimen collection labels are completed and filled in correctly. Enter information from the Blood Specimen Submission Form.
- 14.162 Ship all plasma and white blood cells via Priority Overnight service on dry ice.
- 14.163 Ship specimens via Priority Overnight service, **Monday – Friday**, to BAP Freezer according to kit instructions. **Do not send samples on weekends or just prior to federal holidays.**
- 14.164 The BAP kits will include a smart shipper label (3x5 white barcoded label) affixed to the shipping boxes. The smart shipper label is a pre-addressed return label, which replaces the need for an airbill. Shipping costs will be covered by ACCRU if the shipping box provided with the BAP kit is used for shipping specimens to BAP Freezer.
- 14.165 BAP Freezer will receive the samples and immediately forward specimens to the ACCRU Research Base BAP Shared Resource, [name], Attention: BAP Supervisor.

14.2 Study Methodology and Storage Information

14.21 Blood/blood product samples will be collected for pharmacokinetic analysis.

PK analysis for regorafenib and M2 and M5 will be performed as follows:

- Cycle 1 day 7: 0, prior to dosing (C_{min} , trough levels)
- Cycle 1 day 14: 0, prior to dosing (C_{min} , trough levels)
- Cycle 1 day 21: 0, prior to dosing (C_{min} , trough levels)
- Cycle 2 day 1: 0, prior to dosing (C_{min} , trough levels)
- Cycle 2 day 21; 0, prior to dosing (C_{min} , trough levels)
- Window sampling times are predose \leq 12 hours.

14.211 A portion of the plasma, 0.5 ml (500 μ l), for each sample will initially be analyzed for the amount of regorafenib in [name] laboratory using standard laboratory protocols. The samples will be shipped upon request to

[REDACTED]

[REDACTED]

According to patient consent information, remaining white blood cells/plasma will be stored frozen at -70/-80°C by BAP until specific analyses are identified. As protocols are developed, they will be presented for ACCRU and IRB review and approval. (This collection is part of a general strategy of investigation for the majority of ACCRU studies.)

- 14.212 Ongoing research is likely to identify putative biomarkers for regorafenib efficacy and/or toxicity in the near future. Given the key importance of such biomarker identification, our study offers a unique opportunity to validate such discoveries given its size and prospective nature. As such, and as part of ongoing ACCRU research, we will collect plasma and white blood cells for future research studies, according to patient consent information, on molecular determinants of efficacy and tolerability. Samples will be stored frozen at -70°C by BAP until specific analyses are identified. As protocols are developed, they will be presented for ACCRU (scientific) and IRB review and approval prior to any samples being used.

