1.3 Correlative Research

1.31 Regorafenib clinical pharmacokinetics

Regorafenib and its metabolites M2 and M5 have been assessed pharmacokinetically in several phase I studies, both with regorafenib dosed 21 days on/7 days off (Mross K et al. 2012; Strumberg D et al. 2012; Sunakawa Y et al. 2014), and with continuous dosing (Kies MS et al. 2010; Finn RS et al. 2013). Based on safety, efficacy and PK analysis (higher exposure on dosing days), the final dose taken into phase III studies was 160 mg 21 days on/7 days off.

Regorafenib is moderately fast absorbed after oral administration with median t_{max} of 3 to 4 hours, and mean C_{max} of 2.5 mg/L. Steady-state is expected to occur within 7 days after first administration. The overall mean terminal half-life at steady state is 20-30 hours, with a $t_{max,ss}$ of 5 hrs. Mean $C_{max,ss}$ and $AUC_{(0-24)ss}$ with 160 mg dosing were 3.9 mg/L and 58.3 mg•h/L. In the dose escalation phase I studies, regorafenib PK at doses above 60 mg was less than dose proportional. Accumulation of regorafenib from day 1 to day 21 was consistent with linear pharmacokinetics (Mross K, et al .2012).

Regorafenib has 2 major active metabolites, M2 and M5. While both regorafenib and M2 have elimination half-lives of 20-30 hrs, the M5 active metabolite has a half-life of 60 hrs (range 40-100 hrs).

Regorafenib and its active metabolites have substantial variability in their plasma exposure – expressed as either the maximum concentration shortly after administration (C_{max}) or the area under the concentration-time curve (AUC) – after oral regorafenib administration. The coefficient in variation (standard

deviation/mean) of C_{\max} ranges from 61.9% to 173.5%, showing considerable interpatient variability in the absorption. This is not unexpected since regorafenib's absorption is influenced by the fat content in the diet (Section 15.15). Similarly, the AUC has substantial variability with the CVs ranging from 77.8 to 182.4%. This is also not unexpected since regorafenib undergoes enterohepatic recirculation, and is susceptible to a multitude of drug interactions since it is a CYP3A4 and UGT1A9 substrate (Section 15.15). Furthermore, within-patient variability is present such that an individual patient can have dose-to-dose variability in their pharmacokinetics.

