7.0 Protocol Treatment

7.1 Treatment Schedule

Arm	Agent	Dose	Route	Frequency	ReRx
A 1	Regorafenib	80 mg daily (Starting dose) See Section 7.11	PO	Daily for 21 days of 28 day cycle	Every 28 days
	Clobetasol (pre-emptive)	0.05% cream thin layer to palms and soles, avoid washing hands or feet for 1 hour after application	Topical	BID for first 12 weeks	BID for first 12 weeks starting Day 1 of regorafenib dose
A 2	Regorafenib	80 mg daily (Starting dose) See Section 7.11	PO	Daily for 21 days of 28 day cycle	Every 28 days
	Clobetasol (reactive)	0.05% cream thin layer to palms and soles, avoid washing hands or feet for 1 hour after application	Topical	BID (per physician discretion; recommend no longer than 12 weeks from initiation)	BID (per physician discretion upon occurrence of PPES Grade ≥ 1 ; recommend no longer than 12 weeks from initiation)
B 1	Regorafenib	160 mg (Starting dose)	PO	Daily for 21 days of 28 day cycle	Every 28 days
	Clobetasol (pre-emptive)	0.05% cream thin layer to palms and soles, avoid washing hands or feet for 1 hour after application	Topical	BID for first 12 weeks	BID for first 12 weeks starting Day 1 of regorafenib dose
B 2	Regorafenib	160 mg (Starting dose)	PO	Daily for 21 days of 28 day cycle	Every 28 days
	Clobetasol (reactive)	0.05% cream thin layer to palms and soles, avoid washing hands or feet for 1 hour after application	Topical	BID (per physician discretion; recommend no longer than 12 weeks from initiation)	BID (per physician discretion upon occurrence of PPES Grade ≥ 1 ; recommend no longer than 12 weeks from initiation)

Regorafenib tablets should be taken once a day with approximately 8 fluid ounces (240 mL) of water after a low-fat (<30% fat) meal. Regorafenib should be taken with a meal at the same time every day. Some examples of low fat meals are:

- Two slices of white toast with 1 tablespoon of low-fat margarine and 1 tablespoon of jelly and 8 ounces (240 mL) of skim milk (approximately 319 calories and 8.2 g of fat).

- One cup of cereal (i.e. Special K), 8 ounces (240 mL) of skim milk, one piece of toast with jam (no butter or marmalade), apple juice, and one cup of coffee or tea (2 g fat, 17 g protein, 93 g of carbohydrate, 520 calories).

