- b) Distribution – Regorafenib undergoes enterohepatic circulation with multiple plasma concentration peaks observed across the 24-hour dosing interval. Regorafenib is highly bound (99.5%) to human plasma proteins.
- c) Metabolism – Regorafenib is metabolized by CYP3A4 and UGT1A9. The main circulating metabolites measured at steady state are M-2 (N-oxide) and M-5 (N-oxide and N-desmethyl), both of them having similar *in vitro* pharmacological activity and steady-state concentrations as regorafenib. M-2 and M-5 are highly protein bound (99.8% and 99.95%, respectively).

d) Excretion – Elimination half-lives for regorafenib and the M-2 metabolite in plasma are 28 hours (14 to 58 hours) and 25 hours (14 to 32 hours), respectively. M-5 has a longer mean (range) elimination half-life of 51 hours (32 to 70 hours). Elimination occurs through: Feces (71%; 47% as parent compound; 24% as parent compound; 24% as metabolites); Urine (19%).

15.16 **Potential Drug Interactions:** Avoid concomitant use of strong CYP3A4 inducers (i.e. rifampin, phenytoin, carbamazepine, phenobarbital and St. John's Wort) and strong CYP3A4 inhibitors (i.e. clarithromycin, grapefruit juice, itraconazole, ketoconazole, posaconazole, telithromycin and voriconazole).

15.17 **Known potential toxicities:**

Serious Adverse Effects:

Hepatotoxicity: [U.S. Boxed Warning]: Severe liver toxicity and hepatic failure (sometimes resulting in death) have been observed in clinical trials; hepatocyte necrosis with lymphocyte infiltration has been demonstrated with liver biopsy. Monitor hepatic function at baseline and during treatment. Interrupt therapy for hepatotoxicity; dose reductions or discontinuation are necessary depending on the severity and persistence.

Most Common Adverse Events, >10%

Cardiovascular: Hypertension

Central nervous system: Fatigue, dysphonia, pain, fever, headache.

Dermatologic: Palmar-plantar erythrodysesthesia, rash, alopecia

Endocrine & metabolic: Hypocalcemia, hypophosphatemia, hyponatremia, hypokalemia, hypothyroidism

Gastrointestinal: Appetite decreased, lipase increased, diarrhea, mucositis, weight loss, amylase increased, nausea, vomiting

Hematologic: Anemia, lymphopenia, thrombocytopenia, INR increased, hemorrhage, neutropenia

Hepatic: AST increased, ALT increased, hyperbilirubinemia

Neuromuscular & skeletal: Stiffness

Renal: Proteinuria

Miscellaneous: Infection

Less Common Adverse Events, 1% - 10%

Cardiovascular: Myocardial ischemia and infarction

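### Section 14.21 counts any sample drawn up to 12 hours pre-dose as C_min and Section 16.47 ignores time since dose; the clearest harm is to the within-patient max:min trough ratio

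*Combined protocol and SAP*

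**What the plan says.** Section 14.21 lists five draws (Cycle 1 days 7, 14 and 21; Cycle 2 days 1 and 21), each labelled as a time-zero trough, for example "Cycle 1 day 7: 0, prior to dosing (C_{min} , trough levels". It then adds "Window sampling times are predose \leq 12 hours". Nothing elsewhere in the document narrows this. On dosing, Section 7.1 says "Regorafenib tablets should be taken once a day", at a consistent time, but fixes no hour of the day.

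On timing records, Section 14.14 says "Label specimen tube(s) with protocol number, ACCRU patient ID number, and time and date blood is drawn and sample type". That gives the time of the draw. The visible text does not ask for the time of the previous dose at the draw.

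Section 16.47 averages regorafenib concentration by arm at each nominal time point and correlates it, as exploratory work, with toxicity and efficacy. It also describes within-patient variability of troughs by the ratio of the largest to the smallest value, overall and within cycles. Time since the last dose does not appear in any of these analyses.

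On kinetics, Section 1.31 says "The overall mean terminal half-life at steady state is 20-30 hours" and gives M5 a half-life of 60 h (40-100 h). Section 15.15 adds "Regorafenib undergoes enterohepatic circulation with multiple plasma concentration peaks observed across the 24-hour dosing interval".

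**The concern.** With a 24-hour interval, 12 hours before the next dose is 12 hours after the last one. That is about 7 hours after the steady-state t_max of 5 h given in Section 1.31. A patient who doses in the evening and is bled at a morning clinic can sit near that limit. A patient who holds a morning dose until after the draw gives a true trough. Both results are stored and analysed as the same quantity.

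The time from dose to draw therefore becomes an unmeasured component of C_min. It could add error to the arm comparison (goal 2.31), weaken the correlations with toxicity, response, PFS and OS (goals 2.31 to 2.33), and pass for biological variation in the within-patient ratio. Section 1.32 calls it critical to judge whether PK variability matters clinically, so a variability measure that partly reflects clinic scheduling would miss its purpose.

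**Working it through.** The plan gives no figure for the effect of the window, so there is nothing to reproduce first.

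**Inputs.** Window 12 h (14.21); interval 24 h (7.1); half-life 20-30 h for regorafenib and M2, and 60 h (40-100 h) for M5 (1.31); regorafenib 28 h with range 14-58 h (15.15); between-patient CV of AUC 77.8-182.4% and of C_max 61.9-173.5% (1.31).

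**1. Edge of the window.** Under first-order decline, the level w hours before the dose divided by the trough is 2^(w/t_half). For w = 12:

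| Analyte | Half-life (h) | Ratio to trough |
|---|---|---|
| Regorafenib, M2 | 30 | 2^(12/30) = 1.320 |
| Regorafenib, M2 | 20 | 2^(12/20) = 1.516 |
| Regorafenib, range in 15.15 | 58 to 14 | 1.154 to 1.811 |
| M5 | 100 / 60 / 40 | 1.087 / 1.149 / 1.231 |

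A steady-state one-compartment oral model, with absorption set so that t_max is 5 h, gives 1.316 at 30 h and 1.507 at 20 h. The simple formula is adequate.

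**2. Average over the window.** If draws were spread evenly over 0-12 h (an assumption), the mean ratio is (2^(12/t) - 1) / ((12/t) ln 2). At 30 h this is 0.3195/0.2773 = 1.152. At 20 h it is 0.5157/0.4159 = 1.240.

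**3. Samples near the trough.** For w = 2 the excess is 4.7% at 30 h and 7.2% at 20 h.

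**4. Cycle 2 Day 1.** If dosing ended on day 21, this draw falls 8 days (192 h) after the last dose. Relative to a 24 h trough, 2^(-168/20) = 0.003 to 2^(-168/30) = 0.021 of the level remains. A 12 h shift then changes the result by 0.003 x 0.516 = 0.15% to 0.021 x 0.320 = 0.7% of the steady-state trough. For M5 at 60 h, the figures are 2^(-168/60) = 0.144 remaining and 0.144 x 0.149 = 2.1%.

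**5. Exposure-outcome correlations.** Assume that trough variability is lognormal with the stated AUC CVs. The log-SD is sqrt(ln(1 + CV^2)) = 0.69 to 1.21.
- Even spread over 12 h: added log-SD = (12/t) ln 2 / sqrt(12) = 0.08 (30 h) to 0.12 (20 h). Variance rises by 0.4-3% and a correlation is multiplied by 0.985-0.998.
- Half the draws at 0 h and half at 12 h: added log-SD = (12/t) ln 2 / 2 = 0.14 to 0.21. Variance rises by 1.3-9% and the multiplier is 0.957-0.994.
- With the smallest stated C_max CV instead (61.9%, log-variance ln(1 + 0.619^2) = 0.324) and the worst split at 20 h (added variance 0.208^2 = 0.043), the multiplier is 1/sqrt(1 + 0.043/0.324) = 0.94.

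**6. Within-patient max:min ratio.** At constant dose with no biological variation, one draw at 0 h and another at 12 h give 1.32-1.52 instead of 1.00. If the dose-to-draw time moves by 8 h between visits, the ratio is 2^(8/30) = 1.20 to 2^(8/20) = 1.32. The cleanest case is Arm B, Cycle 1, for patients held at one dose. A ratio that includes Cycle 2 Day 1 is dominated by the week off (about 2^(168/30) = 49 to 2^(168/20) = 338 for regorafenib), so timing matters only for the on-treatment draws.

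**The case against.** The strongest reply is that the window is a reasonable trade. Section 1.32 says the schedule was built to be easy for clinics and to keep patients compliant. Between-patient variability is so large that 12 hours of slack costs the exposure-outcome correlations about 4% at worst on the AUC CVs, usually 1-2% or less. Those correlations are labelled exploratory. A hard 2-hour limit would drop evening dosers from every on-treatment trough summary if clinics draw by day. All of this stands, and it is why the window should not simply be tightened.

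Four stronger readings are tempting, and the documents do not support them:
- **That the arm comparison is biased.** Arms are randomised and share the same schedule and window. Any upward shift is expected to be proportionally the same in both, leaving noise.
- **That 32-52% is the typical error.** It is the edge of the window under smooth decline. The multiple peaks in Section 15.15 could make the true figure smaller or larger.
- **That dose times are not captured.** The tube label carries only the draw time, but the medication diary (Appendix II) and the Blood Specimen Submission Form are not in the available text, and either may record it.
- **That false associations with patient factors (goal 2.34) will follow.** This would need dosing hour to be linked to age or concomitant medication, and nothing in the documents says so.

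The reply does not rescue the within-patient ratio. Large differences between patients do not mask timing error in a measure taken within a patient. Dosing at a consistent time limits the problem, since a patient always bled at the same hour would show no inflation, but the plan does not fix the hour of the draw.

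**Conclusion.** The point holds as a cheap improvement to the correlative analysis. Section 14.21 accepts as C_min samples that may lie about 32-52% above the trough for regorafenib and M2 at the window edge, and about 9-23% for M5. The average is about 15-24% for regorafenib and M2 if draws spread evenly. In absolute terms the effect at Cycle 2 Day 1 is negligible. The A versus B comparison gains noise, not bias, and the exposure-outcome correlations lose little. The clearest harm is to the within-patient max:min ratio, which timing alone could take to about 1.3-1.5 at constant dose if the dose-to-draw time shifts by the full 12 hours between visits.

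These sizes rest on first-order decline from 12 to 24 h, the half-lives in Section 1.31, AUC and C_max variability as stand-ins for trough variability, and dosing that ended on day 21 for the Cycle 2 Day 1 figure. The primary endpoint is unaffected.

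**What to change.** - **Data.** Confirm that the diary or the Blood Specimen Submission Form records the date and clock time of the previous dose at each PK draw. If neither does, add that field.
- **Section 14.21.** Keep the 12-hour collection window, so that no samples are lost.
- **Section 16.47, main analysis.** For the on-treatment draws (Cycle 1 days 7, 14 and 21; Cycle 2 day 21), analyse log concentration with actual time since last dose as a covariate, or normalise to 24 h post-dose. Compute the within-patient max:min ratio from these adjusted values, and report Cycle 2 Day 1 separately as a level after the week off.
- **Section 16.47, sensitivity.** Add a summary limited to samples near the end of the interval, for example within 2 h pre-dose, where the excess under the same model is 4.7-7.2%.

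The cost is one form field if it is not already there, a few sentences in Section 16.47, slightly more analysis work, and reliance on patient-reported dose times. No extra visit or draw is needed.

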14.3 Return of Genetic Testing Research Results

For this study, DNA (White Blood Cells) is only being banked, and no specific genetic testing is being performed. If, at any time, genetic results are obtained that may have clinical relevance, IRB review and approval will be sought regarding the most appropriate manner of disclosure and whether or not validation in a CLIA-certified setting will be required. Sharing of research data with individual patients should only occur when data have been validated by multiple studies and testing has been done in CLIA-approved laboratories.

15.0 Drug Information

IND exempt

- Investigator brochure - Available on the ACCRU website.

15.1 Regorafenib (BAY 73-4506, Stivarga®)

15.11 **Background:** Regorafenib is a novel oral multi-kinase inhibitor that targets tumor cells and the tumor microenvironment. It inhibits tumor growth, progression and metastasis by inhibiting the proliferation of tumor cells, the formation of new tumor vasculature and stromal signaling in the microenvironment of the tumor.

15.12 **Formulation:** Regorafenib 40-mg tablets contains regorafenib and the inactive excipients microcrystalline cellulose, croscarmellose sodium, magnesium stearate, povidone, colloidal anhydrous silica, polyvinyl alcohol-part hydrolyzed, talk, titanium dioxide E171 (color index 77891), Macrogol/PEG 33350, lecithin (soy), iron oxide yellow – E172 (color index 77491), iron oxide red – E172.

Regorafenib will be provided by Bayer as coated, not divisible, gray-orange-red, oval tablets (length 16 mm, width 7 mm, thickness 4.9-5.6 mm). Tablets are in an immediate-release dosage form with rapid dissolution characteristics under the *in vitro* test conditions.

Regorafenib tablets will be packaged in high density polyethylene bottles with a white child resistant closure and induction seal. Each bottle includes 28 tablets and a 3-gram desiccant. The bottles will have a label affixed containing study identification, product identification, and quantity of tablets.

15.13 **Preparation and storage:** Once the drug has been received it must be kept in a secure, dry location. Study drug must be stored in its original bottle at a temperature not above 25°C (77°F). The study drug must be exclusively used for the investigation specified in this protocol and it will only be accessible to authorized staff.

15.14 **Administration:** Regorafenib tablets should be taken at the same time every day with approximately 8 fluid ounces (240 mL) of water after a low-fat (<30% fat) meal. Regorafenib should not be taken with grapefruit juice.

15.15 Pharmacokinetic information:

- a) Absorption – A high-fat meal increased the mean AUC of the parent drug by 48% compared to the fasted state and decreased the mean AUC of the M-2 (N-oxide) and M-5 (N-oxide and N-desmethyl) active metabolites by 20% and 51%, respectively. A low-fat meal increased the mean AUC of regorafenib, M-2 and M-5 by 36%, 40% and 23%, respectively (as compared to the fasted state).
- b) Distribution – Regorafenib undergoes enterohepatic circulation with multiple plasma concentration peaks observed across the 24-hour dosing interval. Regorafenib is highly bound (99.5%) to human plasma proteins.
- c) Metabolism – Regorafenib is metabolized by CYP3A4 and UGT1A9. The main circulating metabolites measured at steady state are M-2 (N-oxide) and M-5 (N-oxide and N-desmethyl), both of them having similar *in vitro* pharmacological activity and steady-state concentrations as regorafenib. M-2 and M-5 are highly protein bound (99.8% and 99.95%, respectively).

d) Excretion – Elimination half-lives for regorafenib and the M-2 metabolite in plasma are 28 hours (14 to 58 hours) and 25 hours (14 to 32 hours), respectively. M-5 has a longer mean (range) elimination half-life of 51 hours (32 to 70 hours). Elimination occurs through: Feces (71%; 47% as parent compound; 24% as parent compound; 24% as metabolites); Urine (19%).

15.16 **Potential Drug Interactions:** Avoid concomitant use of strong CYP3A4 inducers (i.e. rifampin, phenytoin, carbamazepine, phenobarbital and St. John's Wort) and strong CYP3A4 inhibitors (i.e. clarithromycin, grapefruit juice, itraconazole, ketoconazole, posaconazole, telithromycin and voriconazole).

15.17 **Known potential toxicities:**

Serious Adverse Effects:

Hepatotoxicity: [U.S. Boxed Warning]: Severe liver toxicity and hepatic failure (sometimes resulting in death) have been observed in clinical trials; hepatocyte necrosis with lymphocyte infiltration has been demonstrated with liver biopsy. Monitor hepatic function at baseline and during treatment. Interrupt therapy for hepatotoxicity; dose reductions or discontinuation are necessary depending on the severity and persistence.

Most Common Adverse Events, >10%

Cardiovascular: Hypertension

Central nervous system: Fatigue, dysphonia, pain, fever, headache.

Dermatologic: Palmar-plantar erythrodysesthesia, rash, alopecia

Endocrine & metabolic: Hypocalcemia, hypophosphatemia, hyponatremia, hypokalemia, hypothyroidism

Gastrointestinal: Appetite decreased, lipase increased, diarrhea, mucositis, weight loss, amylase increased, nausea, vomiting

Hematologic: Anemia, lymphopenia, thrombocytopenia, INR increased, hemorrhage, neutropenia

Hepatic: AST increased, ALT increased, hyperbilirubinemia

Neuromuscular & skeletal: Stiffness

Renal: Proteinuria

Miscellaneous: Infection

Less Common Adverse Events, 1% - 10%

Cardiovascular: Myocardial ischemia and infarction

Gastrointestinal: Taste disturbance, xerostomia, gastroesophageal reflux

Neuromuscular & skeletal: Tremor

Respiratory: Dyspnea

Rare Adverse Events (Important or life-threatening), <1%

Bradycardia, erythema multiforme, gastrointestinal fistula, hypertensive crisis, liver injury (severe), liver failure, reversible posterior encephalopathy syndrome (RPLS), skin cancer (keratoacanthoma, squamous cell carcinoma), Stevens-Johnson syndrome, toxic epidermal necrolysis

15.18 Study agent procurement:

Bayer HealthCare Pharmaceuticals will supply regorafenib tablets to Biologics, Inc. Each participating ACCRU treating location will order the drug from Biologics, Inc. Fax the Drug Order Request Form (found in the forms packet) to:

Each participating ACCRU treating location will be responsible for monitoring the supply of regorafenib and will use the Drug Order Request Form to order additional supplies as needed.

Outdated or remaining drug is to be destroyed on-site as per procedures in place at each institution.

